13.7.2 Medical emergency

In a medical emergency requiring immediate attention, study staff will apply appropriate medical intervention according to standard medical practice.

13.8 Investigator's Safety Responsibilities

The Investigator's responsibilities include the following:

- Monitor and record all AEs, including SAEs, regardless of the severity or relationship to BGB324.
- Determine the seriousness, relationship and severity of each event.
- Determine the onset and resolution of each event.
- Complete an SAE form for each SAE.
- Pursue SAE follow-up information actively and persistently.
- Ensure all AE and SAE reports are supported by documentation in the patient medical records.
- Report SAEs to their local IRB as required by local law.

13.9 Sponsor's Safety Responsibilities

The Sponsor's responsibilities include the following:

- Ongoing safety evaluation of BGB324.
- Reporting of SUSARs to the Regulatory Authorities, main IRB and Investigators according to required timelines.
- Submission of annual updates to the Regulatory Authorities and main IRB.

14 STATISTICAL CONSIDERATIONS

Detailed statistical analysis information will be provided separately in the Statistical Analysis Plan. Any deviations to the planned analyses will be justified in writing and presented within the final clinical study report (CSR). The database lock will take place when all data are reconciled. A single CSR will be generated for this study. All study data will be listed.

14.1 Patient Disposition, Demography and Baseline Disease Characteristics

Patient disposition, including reason for withdrawal will be summarized by dose group.

Demographics and baseline characteristics will be performed on the Safety Analysis Population (see Section 14.2.1). Demographics and disease baseline characteristics, pregnancy test results, medical history and prior medications will be tabulated.

14.2 Safety

14.2.1 Safety analysis population

The Safety Analysis Population will be defined as all patients who receive at least 1 dose of BGB324 or erlotinib.

14.2.2 Methods of analysis

No formal statistical analysis will be performed on safety data. AEs will be coded using the Medical Dictionary for Regulatory Activities (MedDRA) Version 15.0 or above. The number and percentage of patients reporting treatment-emergent AEs will be tabulated by preferred term, system organ class and dose cohort, and further summarized by both CTCAE grade and relationship to study drug. All AEs commencing prior to dosing with study drug will be excluded from the tabulation but will be fully listed. AEs that have missing onset dates will be considered to be treatment-emergent, unless the stop date is known to be prior to the first administration of BGB324.

Separate listings will be produced for DLTs, SAEs, discontinuations due to AEs, and events of \geq Grade 3 severity.

Summary statistics by dose cohort and time point will be produced for vital signs, 12-lead ECG parameters and laboratory safety data, together with changes from baseline. The incidence of laboratory test results showing shifts of more than one CTCAE grade will be summarized

by dose cohort, time point and overall. Laboratory test results outside the normal range will be individually listed for clinical review, including clinical significance and the baseline value. Abnormal ECG results will be summarized by dose cohort. Changes in continuous parameters will be analyzed according to administered dose.

14.3 Efficacy

14.3.1 Efficacy analysis population

The Efficacy Analysis Population will include all patients who receive ≥ 1 cycle of BGB324 and undergo a post-treatment assessment of response.

Patients who on review do not meet the protocol inclusion/exclusion criteria or have a major protocol deviation may be excluded from the efficacy analysis. This will be reviewed on a per patient basis at the pre-database lock meeting.

14.3.2 Methods of analysis

Data relating to efficacy will be summarized descriptively by dose cohort and time point, as appropriate.

Although all efficacy analysis for this study is to be regarded as essentially exploratory, there will be a formal hypothesis test for the objective response rate in Arm B. This will consist of one-sided, within-group tests of proportion of responders, against the null hypothesis of a response rate $\leq 5\%$ (this being the observed response rate under current treatment). Values of $p < 0.2$ will be taken as sufficient evidence of a trend to justify further study.

14.4 Pharmacokinetics

14.4.1 Pharmacokinetic analysis population

The Pharmacokinetic Analysis Population will include those patients in the Run-in Cohort and Arm B who receive at least 1 dose of BGB324 and have PK data available and those patients in Arm A who receive at least 1 dose of BGB324 and erlotinib and have BGB324 and erlotinib PK data available.

14.4.2 Methods of analysis

Full details of analysis of BGB324 PK will be provided in a Pharmacokinetics Analysis Plan. BGB324 plasma concentration-time data will be summarized descriptively (mean, standard deviation and coefficient of variation). Mean plasma profiles will be illustrated in graphical form. An appropriate PK model will be fitted to the individual plasma profiles of BGB324.

Pharmacokinetic parameters of BGB324 that will be estimated are summarized in Table 10. These parameters will be estimated at steady state.

Table 10 BGB324 Pharmacokinetic Parameters to be Evaluated

C_{\max}	The observed maximum plasma concentration after single dose administration
t_{\max}	The time to reach C_{\max}
AUC_{0-t}	The area under the curve within a dosing interval, calculated by the linear up-log down trapezoidal method.

14.5 Pharmacodynamics

14.5.1 Pharmacodynamic analysis population

The Pharmacodynamic Analysis Population will include all patients who receive at least 1 dose of BGB324 and erlotinib and have at least 1 PD biomarker sample collected for analysis.

14.5.2 Methods of analysis

No formal analysis of PD will be performed. Pharmacodynamic biomarker results will be summarized descriptively by dose cohort and timepoint as appropriate.

14.6 Sample Size Considerations

Arm A will utilize a conventional algorithm (3+3 patients per dose level) to identify the dose of BGB324 that can be safely given in combination with erlotinib. Escalation between dose levels will occur if 0/3 or 1/6 patients experiences a DLT. Under this design, there is a 71% chance of escalation if the true but unknown rate of DLT is 20% and <50% chance of escalation if the true but unknown rate of DLT is >30%. The operating characteristics of this 3+3 design are outlined in Table 11.

Table 11 Operating Characteristics of the 3+3 Study Design

True but Unknown Rate of DLT (%)	Probability of Escalation (%)
20	71
30	49
40	31
50	17
60	8

It is anticipated that a maximum of 3 BGB324 dose levels will be evaluated, with up to approximately 18 patients enrolled. The total sample size in Arm A will depend upon whether a DLT is experienced at a given dose level (i.e., whether 3 or 6 patients have been treated) and how many dose levels are tested to reach the dose that can be safely administered in combination with erlotinib.

Arm B will follow a Simon-like 2-stage design with relaxed stopping for futility to evaluate the PK of BGB324 ,safety and tolerability,, PD and clinical efficacy of BGB324 in combination with erlotinib in patients with an activating EGFR mutation(s) (including exon 19 deletion or exon 21 [L858R] substitution or other rearrangement of the EGFR gene mutations) who have progressed after receiving a prior EGFR inhibitor (i.e., erlotinib, afatinib, or gefitinib). The null hypothesis (H_0) that the true response rate is 0.05 will be tested against a 1-sided alternative in the first stage, 9 patients accrued. If the number of patients with response (complete response or partial response) after 2 cycles or stable disease after 4 cycles is equal to zero in these 9 patients, the study will be stopped. Otherwise, 16 additional patients will be accrued for a total of 25. The null hypothesis will be rejected if 4 or more responses are observed in 25 patients. Assuming that the stable disease rate has a uniform distribution under H_0 , this design yields a type I error rate of at most 0.73 and power of at least 0.0367 when the true response rate is 0.2.

Arm C will evaluate the safety, PD and clinical efficacy (time to progression) of BGB324 when administered in combination with erlotinib in patients with activating EGFR mutation(s) (including exon 19 deletion or exon 21 [L858R] substitution or other rearrangement of the EGFR gene mutations) who have received ≥ 12 weeks of erlotinib without disease progression. Up to 5 patients will be enrolled. Arm C will recruit up to a maximum of 14 patients. Recruitment into Arm C may be stopped if Arm B completes recruitment or is stopped before the 14 patient target is reached. Patients already enrolled into Arm C will be allowed to continue in the study in accordance with the protocol. A statistical analysis is not planned and it is anticipated that an assessment of general activity will be derived from the enrolled patients; further assessment will require protocol amendment.

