5.7.3 Method of analysis for efficacy outcome

5.7.3.1 Objective Response Rate (ORR)

Response criteria for target lesions and non-target lesions (see [Section 3.2](#)) will be evaluated at each disease assessment and will be presented in a data listing by subject.

In addition, the presence/absence of new lesions will be collected at each disease assessment and will be presented in a data listing by subject.

The investigator will evaluate the target/non-target lesion response criteria and status (presence/absence) of new lesions against the RECIST Version 1.1 criteria to determine overall response for the appropriate disease assessment time point.

Although all efficacy analysis for this study is to be regarded as essentially exploratory, there will be a formal hypothesis test for the objective response rate here (Arm B only). Specifically, for a given disease assessment time point we denote subjects who achieve a CR or a PR Best overall response. The null hypothesis is that the proportion of objective responders (i.e., the ORR) is less than or equal to 5%. The alternative hypothesis is that the proportion of objective responders is greater than 5%. The binomial test will be used to conduct the hypothesis test at the one-sided significance level of 0.2.

Overall response and the ORR will be presented within a data listing by subject and time point.

Best overall Response (BOR) will also be listed.

The number and percentage of each BOR class will be described by cohort.

Moreover, the Sum of Target Lesion Measurements (STLM) will be analyzed from relative changes from baseline and graphically displayed with waterfall plot in order to visualize changes in sum of lesion without differentiating best response categories.

Best response to therapy will be defined as the Best Changes from Baseline in Sum of Target lesions measurement for a patient during the study.

The Best Percentage change in STLM will be calculated as, $STLM = 100 * (\text{Value of STLM} - \text{Baseline value STLM}) / \text{Baseline value STLM}$;

In case of several post baseline assessments of STLM the one with the lowest change (i.e., showing the best diminution of sum of lesions relative to baseline) will be considered.

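### Arm B's stated type I error (at most 0.73) and power (at least 0.0367) appear transposed; the written rule gives about 0.034 and 0.76, and a second success criterion conflicts with it

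*Protocol*

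**What the plan says.** Protocol 14.6 sets up Arm B as a two-stage test of a 5% response rate: the null hypothesis "that the true response rate is 0.05 will be tested against a 1-sided alternative in the first stage, 9 patients accrued". Recruitment stops if the count of first-stage patients with a response after 2 cycles or "stable disease after 4 cycles is equal to zero in these 9 patients, the study will be stopped". Otherwise 16 more are added, and "The null hypothesis will be rejected if 4 or more responses are observed in 25 patients". It then says that, with the stable-disease rate taken as uniform under the null hypothesis, "this design yields a type I error rate of at most 0.73 and power of at least 0.0367" at a true response rate of 0.2. SAP 4.9 repeats the rule and both figures.

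The same test has a second success criterion elsewhere. Protocol 14.3.2, the Protocol synopsis (Statistical Methods) and SAP 3.2.1 describe a one-sided test against a rate of 5% or less, in which p < 0.2 "will be taken as sufficient evidence of a trend to justify further study". SAP 5.7.3.1 makes this a formal level: "The binomial test will be used to conduct the hypothesis test at the one-sided significance level of 0.2".

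**The concern.** A type I error bound of 0.73 beside a power bound of 0.0367 describes a test that is more likely to succeed when the drug does nothing than when it works. A rule that rejects on a high response count cannot behave that way. The magnitudes suggest that the two labels were exchanged.

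This is the only power statement for the only formal hypothesis test in the trial. A reader who takes it at face value is told that an inactive combination could be declared active up to 73% of the time. The correct replacement also depends on which rejection rule governs, and the documents give two.

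**Working it through.** **Inputs (Protocol 14.6, repeated in SAP 4.9).** Null rate 0.05; alternative 0.20; one-sided; first stage 9; total 25; reject at r = 4 or more responses; stop if 0 of 9 have a response or stable disease. The range of the uniform stable-disease rate is not given. I take it as 0 to 1-p, under both hypotheses, and show other ranges. All 25 patients are counted.

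**Formula.** With response rate p and stable-disease rate s, the chance that no first-stage patient has either is (1-p-s)^9. Stopping loses only those trials that would have reached r responses from the last 16 patients alone:

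P(reject) = P(X ≥ r | 25, p) − (1−p−s)^9 × P(X ≥ r | 16, p)

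This is lowest at s = 0 and highest when the trial never stops. Averaged over s uniform on 0 to 1-p, (1-p-s)^9 becomes (1-p)^9 / 10.

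**Numbers for r = 4**

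| | p = 0.05 (type I error) | p = 0.20 (power) |
|---|---|---|
| P(X ≥ 4 \| 25), never stops | 0.0341 | 0.7660 |
| P(X ≥ 4 \| 16) | 0.0070 | 0.4019 |
| (1-p)^9 | 0.6302 | 0.1342 |
| No stable disease | 0.0341 − 0.6302 × 0.0070 = 0.0297 | 0.7660 − 0.1342 × 0.4019 = 0.7121 |
| Uniform on 0 to 1-p | 0.0341 − 0.0630 × 0.0070 = 0.0336 | 0.7660 − 0.0134 × 0.4019 = 0.7606 |

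A simulation of 2,000,000 trials under the uniform assumption gave 0.0336 and 0.760.

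**Can the printed figures be reproduced?** No stable-disease rate makes this rule attain 0.73 at p = 0.05 or 0.0367 at p = 0.20. Counting stable disease towards the final cut-off gives 0.877 and 0.976. Single-stage cut-offs of 3 and 5 do not match either. A search of neighbouring designs (first stage 5 to 15, total up to 40, cut-off 2 to 7) found none that gives 0.0367 and 0.73 together.

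**Do they hold with the labels exchanged?** As bounds under the uniform 0 to 1-p assumption, yes: 0.0336 ≤ 0.0367 and 0.761 ≥ 0.73. They are not the design's values. The type I error can never reach 0.0367, since its maximum is 0.0341. Power falls below 0.73 once the true stable-disease rate is under 0.0351.

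**Sensitivity to the unstated range (r = 4, averages)**

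| Uniform range of s | Type I error | Power |
|---|---|---|
| 0 to 1-p | 0.0336 | 0.761 |
| 0 to 0.5 | 0.0333 | 0.757 |
| 0 to 0.3 | 0.0327 | 0.752 |
| 0 to 0.1 | 0.0313 | 0.734 |

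Averaged power drops below 0.73 only if the range ends below about 0.075.

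**The competing criterion.** One-sided exact p-values for 25 patients against 5%: 2 responses, 0.358; 3 responses, 0.127; 4 responses, 0.034. So p < 0.2 is met at 3 of 25. With r = 3 the same formula gives type I error 0.1000 to 0.1271 and power 0.8148 to 0.9018 (0.1244 and 0.8931 for s uniform on 0 to 1-p).

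**The case against.** - **Severity.** Arm B's primary objective is safety, efficacy is called exploratory, and the sample sizes and cut-off are printed, so a statistician can recover the true figures. That stands as far as conduct goes: nothing done to patients changes. It does not excuse an uninformative error rate and power for the one formal test, in both documents, when the correction is a sentence.
- **Literal reading.** Taken strictly as inequalities, the printed bounds are not violated: 0.0341 is below 0.73 and 0.712 is above 0.0367. But bounds that loose say nothing about the design, and cannot be what was meant.
- **Transposition is inferred.** True. It rests on magnitude and on both bounds holding under the uniform assumption once exchanged. That the printed figures do not describe the rule needs no inference.
- **The p < 0.2 wording could coexist with a stricter rejection rule.** Protocol 14.3.2 speaks of a trend that justifies further study, which might be a lower bar. However, it attaches that bar to the formal test itself, and SAP 5.7.3.1 names 0.2 as the significance level. The conflict is real.
- **The recomputed floor is conditional.** This stands as a qualifier. The SAP's response rate uses the Efficacy Population, which may be smaller than 25; even without stopping, power for 4 or more responses is 0.703 at 23 patients and 0.668 at 22. Protocol 8.4 also words the futility check as evidence after 4 cycles, without the separate 2-cycle response criterion of 14.6. If an early responder who has progressed by then does not count, power is lower: for illustration, with no stable disease and 80% of responders still qualifying, 0.661. The figures above describe the design as 14.6 states it.

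**Conclusion.** The concern holds. Protocol 14.6 and SAP 4.9 misstate Arm B's operating characteristics, evidently with the labels exchanged. For 25 counted patients and the futility rule in 14.6, rejection at 4 or more responses has type I error 0.0297 to 0.0341 and power 0.712 to 0.766. With stable disease uniform on 0 to 1-p under both hypotheses, the values are 0.034 and 0.76. A bare swap is not enough: it leaves loose bounds, and the power bound depends on a range the documents do not give and on an assumption they state only under the null.

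The figures cannot be finalised until one rejection rule is chosen, because 3 of 25 succeeds under the 0.2 criterion and fails under the 4-or-more rule. The misprint does not alter the stated decision rule or trial conduct, but it must be corrected.

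**What to change.** 1. Decide whether 4 or more of 25, or p < 0.2 (met at 3 of 25), governs Arm B. Use that rule in the Protocol synopsis, Protocol 14.3.2 and 14.6, and SAP 3.2.1, 4.9 and 5.7.3.1.
2. State the range of the uniform stable-disease distribution, and that it applies under both hypotheses.
3. Replace the sentence in Protocol 14.6 and SAP 4.9 according to the rule chosen:
   - *4 or more:* type I error at most 0.0341 and power at least 0.71 for any stable-disease rate (0.034 and 0.76 if that rate is uniform on 0 to 1-p under both hypotheses) when the true response rate is 0.2.
   - *3 or more:* type I error at most 0.1272 and power at least 0.81 for any stable-disease rate (0.124 and 0.893 under the same assumption) when the true response rate is 0.2.

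   If another range is stated, recompute the bracketed pair. It would help to add that the figures assume 25 evaluable patients and the futility rule as worded in 14.6.

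The cost is one decision, one sentence in each of the two sample-size sections, and matching lines in the other sections named. Patients and procedures are unaffected.

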STUDY DESIGN	
This is a multi-center, multi-arm open-label Phase 1/2 study that will be conducted at approximately 10 clinical sites; the number of sites may be revised to reflect changes in recruitment rates.
 
Up to 60 patients with histologically- or cytologically-confirmed Stage IIIb or Stage IV NSCLC will receive BGB324 as a single agent (Run-in Cohort) or in combination with erlotinib (Arms A, B and C).
 
At the time of Amendment 5, patient recruitment into the Run-In Arm (BGB324 monotherapy) and Arm A (BGB324 dose escalation in combination with erlotinib) was complete and the RP2D has been confirmed. Patients that remain on treatment in the Run-in Cohort or Arm A should be followed up in accordance with the protocol schedule.

Run-in Cohort (Phase 1)

Prior to commencing dosing of BGB324 in combination with erlotinib, the safety and tolerability of single agent BGB324 will be assessed in a minimum of 6 patients. The safety data from the first cycle in these 6 patients will be reviewed by the safety monitoring committee (SMC) before enrolment into Arm A can commence.

Arm A (Phase 1)

Arm A is designed to determine the daily dose and loading schedule of BGB324 that can be safely administered in combination with erlotinib in patients who have received prior treatment with erlotinib. The starting dose of erlotinib will be 150mg daily. Lower doses of erlotinib may be explored at the request of the SMC. In addition to safety and tolerability, the pharmacokinetics (PK) and pharmacodynamics (PD) of BGB324 and erlotinib will be evaluated.

In Arm A, dose and dosing schedules will be explored to assess tolerability of the loading and daily doses and to select the RP2D for expansion into Phase 2 (Arms B and C).

The dose of BGB324 will be escalated in a standard 3+3 design. The starting dose level of BGB324 will be 600 mg loading dose (2 days) and 200 mg daily dose. It is anticipated that a maximum of 3 BGB324 Dose Levels will be evaluated with up to 18 patients enrolled. Alternative loading dose schedules may be explored in combination with daily dosing schedules (see Table 4).

Dose escalation may be stopped prior to achieving the maximum tolerated dose (MTD) if it is considered that a clinically acceptable recommended Phase 2 dose (RP2D) has been achieved. Safety will be reviewed by the Safety Monitoring Committee (SMC).

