	
a tumour biopsy. Both the blood test/biopsy should be undertaken in accordance with local procedures and do not require central analysis. For patients to be eligible for Arm B, a negative EGFR T790M result must be documented. Patients who have previously been treated with a T790M inhibitor (i.e., osimertinib) and who subsequently progressed will not require T790M testing.
 
If clinical response (complete response or partial response) or disease control (stable disease) is not evident after 4 cycles of treatment in at least 1 patient among the first 9 patients, no further patients will be enrolled. If at least 1 patient in the first 9 patients demonstrates evidence of clinical response or disease control, an additional 16 patients will be enrolled.
 
Recruitment will continue whilst data from the first 9 patients are being analyzed. Thus, up to 25 patients are anticipated to be enrolled in Arm B.
 
Arm C (Phase 2)
 
Arm C will evaluate the safety and tolerability, PD, and clinical efficacy (time to progression) of BGB324 when administered in combination with erlotinib in patients with an activating EGFR mutation who have received ≥ 12 weeks of erlotinib without disease progression. Up to 14 patients will be enrolled. Recruitment into Arm C may be stopped if Arm B completes recruitment or is stopped before the 14 patient target is reached. Patients already enrolled into Arm C at this time will be allowed to continue in the study in accordance with the protocol.
 
In all parts of the study, patients will be allowed to continue BGB324 treatment (in combination with erlotinib or as a single agent) for as long as, in the opinion of the Investigator, they continue to derive clinical benefit or until unacceptable toxicity, disease progression, death or withdrawal of consent.
 
In the event of erlotinib-related toxicities in Arms A, B, or C, patients who stop treatment with erlotinib will be allowed to continue receiving BGB324 as a single agent until disease progression (unless unacceptable toxicity, disease progression, death or withdrawal of consent). Patients who stop BGB324 treatment will be withdrawn from the study.

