8 STUDY DESIGN

8.1 Overview

This is a multi-center open-label Phase 1/2 study of BGB324 as a single agent (Run-in Cohort) and in combination with erlotinib (Arms A, B and C) in patients with Stage IIIb or Stage IV NSCLC.

At the time of Amendment 5, patient recruitment into the Run-In Cohort (BGB324 monotherapy) and Arm A (BGB324 dose escalation in combination with erlotinib) has completed and the RP2D has been confirmed. Patients that remain on treatment in the Run-in Cohort or Arm A must be followed up in accordance with the protocol schedule.

This study is anticipated to be conducted at approximately 10 sites in the US and in Europe (the number of sites and the involvement of European sites may be revised to reflect changes in recruitment rates), and will enroll approximately 60 patients with histologically- or cytologically-confirmed Stage IIIb or Stage IV NSCLC.

It is anticipated that up to 6 patients will be enrolled in the Run-in Cohort, 18 patients in Arm A, up to 25 patients in Arm B, and up to 14 patients in Arm C. Recruitment into Arm C may be stopped if Arm B completes recruitment or is stopped before the 14 patient target is reached. Patients already enrolled into Arm C at that time will be allowed to continue in the study in accordance with the protocol

Prior to starting dosing of BGB324 in combination with erlotinib, the safety and tolerability of single agent BGB324 will be assessed in the Run-in Cohort (Phase 1) in patients who have either exhausted existing licensed therapies or are unsuitable for existing licensed therapies for NSCLC. A minimum of 6 patients must each receive at least 1 continuous 21-day cycle of BGB324 before enrolment into Arm A can commence.

Arm A (Phase 1) incorporates a standard 3+3 design to determine the dose of BGB324 that can be safely administered in combination with erlotinib in patients who have received prior treatment with erlotinib. To confirm the RP2D for Arms B and C, loading dose schedules,

loading doses and daily dose levels will be explored in Arm A. Dosing schedules will be revised in response to reported toxicities, DLT experience and SMC recommendations (Table 4).

When the RP2D dose of BGB324 is identified and the dose of erlotinib to be administered in combination with BGB324 is confirmed, the Phase 2 part of the study will start and Arms B and C will open simultaneously to enrolment.

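### The sample-size sections cap Arm C at both 5 and 14 patients; 14 is the figure everywhere else, and the arm maxima total 63 against the synopsis cap of 60

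*Protocol*

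**What the plan says.** On Arm C, Protocol 14.6 states in two consecutive sentences: "Up to 5 patients will be enrolled. Arm C will recruit up to a maximum of 14 patients". SAP 4.9 carries the same two sentences. Later in the same paragraph, both documents refer to a target of 14 when they describe how recruitment to Arm C may be halted early.

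Elsewhere the figure is always 14. The synopsis says "Up to 14 patients will be enrolled". Protocol 8.1 gives 14 in its list of arm sizes and again in the text with the design figure. Protocol 8.5 and SAP 4.1 also give 14.

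On the total, the synopsis says "Up to 60 patients with histologically- or cytologically-confirmed" Stage IIIb or IV disease. Protocol 8.1 gives a total of approximately 60, and SAP 4.1 gives up to approximately 60. Protocol 8.1 lists the components: "It is anticipated that up to 6 patients will be enrolled in the Run-in Cohort", then "18 patients in Arm A, up to 25 patients in Arm B, and up to 14 patients in Arm C". SAP 4.1 gives the same four numbers.

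**The concern.** The sample-size section is where a site, an ethics board or a programmer looks for the governing number. For Arm C it offers two, and they cannot both be the maximum. Read literally, the first sentence would make a sixth Arm C patient an over-enrolment, while the second allows eight more after that. The SAP copies the conflict, so neither document settles it for the other.

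Arm C has no hypothesis test, but its primary objective is safety and tolerability (Protocol 7.4.1, SAP 2.4.1). The number of patients therefore determines what the arm can show. SAP 5.7.3.2 also plans a Kaplan-Meier estimate of time to progression in this arm, with a median and 95% interval, and that estimate too would be less precise with 5 patients than with 14.

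The total raises a smaller question: whether the overall ceiling in the synopsis leaves room for the arm maxima set out in 8.1.

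**Working it through.** **Which Arm C figure the documents support**

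- Giving 5: one sentence in Protocol 14.6 and its copy in SAP 4.9.
- Giving 14: the next sentence and the later target in those same paragraphs, the synopsis, Protocol 8.1 and 8.5, and SAP 4.1.
- A rule linking 5 to 14 (a first stage, an expansion step or an interim look in Arm C): none in either document. The two-stage rule belongs to Arm B, and the 3+3 rule to Arm A.

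**The study total**

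Inputs from Protocol 8.1: Run-in 6, Arm A 18, Arm B 25, Arm C 14. Arm B agrees with 14.6, where 9 + 16 = 25.

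- With Arm C at 14: 6 + 18 + 25 + 14 = 63, which is 3 above 60 (3/60 = 5%).
- With Arm C at 5: 6 + 18 + 25 + 5 = 54, which is 6 below 60.
- Leaving out the Run-in Cohort, with Arm C at 14: 63 − 6 = 57.
- Arm C size that would give exactly 60: 60 − (6 + 18 + 25) = 60 − 49 = 11, which is stated nowhere.

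The figure of 60 is therefore not the sum of the stated maxima under either Arm C size. Against each statement of the total:

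- Synopsis, a ceiling of 60: 63 exceeds it by 3, and 54 does not exceed it.
- Protocol 8.1, approximately 60: 63 is loosely covered.
- SAP 4.1, up to approximately 60: 63 is loosely covered.

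**What the Arm C size means for safety**

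The 95% level and the 10% event rate below are illustrative choices. The documents give neither for this arm.

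Upper bound on an event rate when none of n patients has the event: solve (1 − p)^n = 0.05, so p = 1 − 0.05^(1/n).

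- n = 5: 1 − 0.05^(1/5) = 0.451, or 45%.
- n = 14: 1 − 0.05^(1/14) = 0.193, or 19%.

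Chance of at least one case when the true rate is 10%: 1 − 0.9^n.

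- n = 5: 1 − 0.9^5 = 0.410, or 41%.
- n = 14: 1 − 0.9^14 = 0.771, or 77%.

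**The case against.** The strongest reply is that nobody would apply the 5. The sentence after it sets a maximum of 14, the same paragraph goes on to a target of 14, and the rest of both documents agrees. A reader might infer that Arm C is at real risk of closing at 5 patients, but the documents do not support that, because the surrounding text overrides the sentence. The contrast between 45% and 19% describes what would be lost if the 5 were followed; it is not a forecast. The contradiction in the governing sections remains.

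On the total, most of the objection stands. A reader might infer that a total of 60 leaves the arms 3 patients short of what they need. No section says that the arms need 63. Protocol 8.1 presents the arm sizes as anticipated, Arm A depends on the toxicities seen, Arm B may stop after its first stage, and Arm C may close when Arm B completes or stops. A study total can properly sit below the sum of such ceilings. The Run-in Cohort and Arm A had also finished recruiting by this version, and their actual numbers are not given, so no shortfall can be established. Nor is it right that every version of the total conflicts: 54 is within a ceiling of 60, and the approximate totals in 8.1 and SAP 4.1 accommodate 63. What is left is the synopsis wording alone.

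It is also fair to object that 63 would not be a dependable hard cap. Protocol 8.1 gives the Run-in Cohort as up to 6 but also says "A minimum of 6 patients must each receive at least 1 continuous 21-day cycle". Protocol 14.6 describes Arm A's 18 as approximate, and 11.7 replaces Arm A patients who leave during Cycle 1 for reasons other than a dose-limiting toxicity.

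**Conclusion.** The Arm C contradiction is certain. It stands in current text in both sample-size sections, and no rule reconciles the two figures. The weight of the documents favours 14, and 5 looks like a remnant, though only the sponsor can confirm that. If the 5 were followed, the zero-event upper bound would be 45% instead of 19%, and the chance of seeing an event with an assumed true rate of 10% would fall from 77% to 41%. The analysis methods are unaffected, since Arm C is descriptive and Protocol 14.6 plans no statistical analysis for it.

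The total is a secondary, editorial matter. The stated arm maxima exceed the synopsis ceiling by 3 patients and conflict with no other statement of the total. The sum rests on taking Arm C as 14 and the Run-in Cohort as 6, with no Arm A replacements counted.

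The correction should be made because it concerns an enrolment figure and is easy to make. It does not call the design into question.

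**What to change.** 1. The sponsor confirms that 14 is the intended Arm C maximum and deletes "Up to 5 patients will be enrolled" from Protocol 14.6 and SAP 4.9.
2. Bring the synopsis total into line with the arm maxima and with Protocol 8.1 and SAP 4.1, using the same wording in all three. One form would be approximately 63 patients, excluding Arm A replacements. Avoid a hard cap of 63, for the reasons given above.

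The cost is a few words in each document and no patients beyond the arm maxima already stated. The protocol part is an amendment, and Protocol 16.5.2 sends every amendment to the IRB and the regulatory authorities, so it is most sensibly included in the next planned one.
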